13.3 Stratification Factors

There are no stratification factors.

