2. BACKGROUND

2.1 Study Disease(s)

Tyrosine kinase inhibitors (TKI) are approved for the management of broad-reaching cancers that include colorectal cancer, renal cell carcinoma, gastrointestinal stromal tumors (GIST), pancreatic neuroendocrine tumor, thyroid and liver malignancies. Such targeted therapies are associated with different adverse events than their cytotoxic predecessors, with a greater frequency of side effects in the skin.

The most frequent toxicities with TKIs are dermatologic, particularly hand-foot skin reaction (HFSR) occurring in all grades in 40-85% of patients on regorafenib¹, 34% of patients on sorafenib² and 19% of patients on sunitinib³; grade 3 HFSR is reported at 13-33%¹, 9%² and 6%³ for each of the drugs respectively. The incidence of HFSR of any grade from regorafenib is highest in renal cell carcinoma (71.4%) followed by GIST (60.2%), hepatocellular carcinoma (50%) and metastatic colorectal carcinoma (46.6%).⁴ Grade-3 toxicity from HFSR is defined by severe skin changes that are painful and may include blisters, bleeding, edema and hyperkeratosis.⁵ Grade-3 toxicities limit self-care activities of daily living (ADLs). Importantly, grade-2 HFSR, a more common event, is also associated with pain, and limits instrumental ADLs. HFSR is one of the most, if not the most, common reason for dose reduction, interruption or discontinuation of regorafenib therapy.^{6,7,8,9}

HFSR has been shown to negatively impact health-related quality of life (HRQOL), more severely with higher-grade disease, as measured using the skindex-16 score, which incorporates symptom, emotion and function domains.¹⁰

Importantly, in the absence of evidence from prospective trials on the prevention of this toxicity, the current recommendation for patients with grade-3 toxicity is to hold the drug until severity declines. When the dose is restarted, it is done so at a lower level. With grade-2 toxicity, dose reduction is considered first line.

Recommendations for supportive care are varied and based primarily on expert opinion or consensus from historical experience with similar eruptions. In the oncology literature, the focus tends to be on how best to reduce doses and reinstitute the TKI.

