2.3 Rationale

There are no clinical or molecular risk factors that have been shown to predict those patients who are predisposed to the development of HFSR. The addition of friction/trauma and heat seems to play a role. Current treatment of HFSR is based on avoiding triggers and treating hyperkeratosis with urea-based products. Urea is a keratolytic and is thought to soften and breakdown thickened skin. There are no studies or trials published to date that attempt to address the underlying pathophysiology of HFSR, rather studies to date have only tried to suppress the clinical features and symptoms.

While, the pathophysiology of HFSR is still being elucidated, there have been a multitude of studies proposing several mechanisms. Some preclinical evidence suggests that there is dysregulation in keratinocyte differentiation, leading to hyperkeratosis, pain and inflammation in the setting of tyrosine kinase inhibition. This clinically and histologically resembles palmoplantar psoriasis in many cases. These findings are supported by the histopathology of HFSR as demonstrated by acanthosis, papillomatosis, hyperkeratosis and necrosis.¹¹ More recently, direct keratinocyte toxicity via anion transporter, OAT6, has been implicated in HFSR in the setting of sorafenib use.¹² Additionally, several studies have implicated the inhibition of anti-angiogenic receptors such as PDGFR and VEGFR in the etiology of HFSR.¹³

Retinoids are vitamin A derivatives that act on the nuclear receptors RAR and/or RXR. These receptors are highly expressed in keratinocytes and control a variety of cellular differentiation functions. Topical tazarotene gel is FDA approved for use in psoriasis, a hyperproliferative cutaneous disorder. Psoriasis shares many clinical and histopathological features with HFSR and both are caused by keratinocyte dysregulation. Tazarotene has been shown to have anti-inflammatory properties and normalize keratinocyte differentiation. Most recently, the RAR receptor blockade, specifically with tazarotene, has been shown to locally promote angiogenesis and may address the anti-angiogenic physiology of HFSR.¹⁴ In our experience, patients with established HFSR have responded to both topical and oral retinoids with marked improvement in symptoms.

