4. REGISTRATION AND RANDOMIZATION PROCEDURES

4.1 General Guidelines for DF/HCC Institutions

Institutions will register eligible participants in the Clinical Trials Management System (CTMS) OnCore. Registrations must occur prior to the initiation of any protocol-specific therapy or intervention. Any participant not registered to the protocol before protocol-specific therapy or intervention begins will be considered ineligible and registration will be denied.

An investigator will confirm eligibility criteria and a member of the study team will complete the protocol-specific eligibility checklist.

Regorafenib is not a drug that is prescribed by the Cutaneous Oncology team. This study's recruitment relies entirely on receiving referrals from other disease centers. Due to the fact that patients are referred from these outside disease centers (such as Sarcoma and GI) and that regorafenib may require insurance clearance and then mailing, we expect that screening and randomization may occur on the same day.

In an effort to increase accrual and more quickly identify potential participants that have been prescribed regorafenib in other departments within the Institute, COC will be utilizing an EPIC report to assist in the recruitment of participants. This report has been built in collaboration with pharmacy to identify patients that have been prescribed regorafenib within the last 7 days. This report can be run by the study team at any time. The COC study team may reach out to the prescribing physician to ask their permission to contact their patient directly to describe this research study and see if they would be interested in participating in this study.

The eligibility checklist(s) and all pages of the consent form(s) will be faxed to the ODQ at [contact]. The ODQ will (a) review the eligibility checklist, (b) register the participant on the protocol, and (c) randomize the participant. ODQ will send the randomization to the research pharmacy.

Randomization can only occur during ODQ business hours (8:30am - 5pm Eastern Time, Monday through Friday excluding holidays).

An email confirmation of the registration and/or randomization will be sent to the Overall PI, study coordinator(s) from the Lead Site, treating investigator and registering person immediately following the registration and/or randomization.

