Clinical and patient demographic factors will be collected. These will include age, gender, BMI, malignancy characteristics, smoking status, occupation, hobbies, activity level, co-morbidities, marital/relationship status, ECOG performance status, prior therapies and prior dermatologic history.

Surveys listed in the study calendar will be delivered in the clinic setting. They may be given in either paper or electronic formats. Every effort will be made to collect the surveys at the required timepoints. Missing data on the questionnaires, either an incomplete or missing survey will be documented but will not be considered a protocol deviation. Survey data will be collected at the designated clinic visits +/- a 3 days window to increase our survey return response rates. Patients may complete the surveys at home, and mail them back to the study team.

The primary endpoint is the development of grade-2 or greater HFSR within 8 weeks of starting protocol therapy. This endpoint is chosen based on its significance of this toxicity grade on ADLs and dose modification. It is the endpoint time used in the reDOS study, as it allows for 2 full cycles of therapy, one with regorafenib dose escalation and one at maximum tolerated dose. It was also chosen to minimize the risk of drop out.

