13.1 Study Design/Endpoints

Endpoints

The primary endpoint will be the proportion of patients in each arm who develop grade-2 or higher HFSR within the first 8 weeks of protocol therapy. A parallel secondary endpoint will be the proportion of patients in each intervention arm who develop HFSR of any grade.

Efficacy Analysis

Primary Endpoint: For each comparison, the proportion of patients with grade-2 or higher HFSR will be compared between placebo gel plus BPS and tazarotene gel plus BPS using a two-group chi-squared test. The difference between the two proportions will be summarized with a 90% confidence interval.

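### The primary test ignores tumour type, which the trial collects and its own background links to HFSR; pre-specified adjustment would bring a small gain at almost no cost

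*Combined protocol and SAP*

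**What the plan says.** Section 13.3 is one line: "There are no stratification factors". Section 13.1 defines the primary endpoint as "the proportion of patients in each arm who develop grade-2 or higher HFSR within the first 8 weeks of protocol therapy" and compares placebo gel plus BPS with "tazarotene gel plus BPS using a two-group chi-squared test". It adds: "The difference between the two proportions will be summarized with a 90% confidence interval". No covariate-adjusted or tumour-type analysis is described anywhere.

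On tumour type, the documents point in two directions. Section 2.1 reports that any-grade HFSR on regorafenib is "highest in renal cell carcinoma (71.4%) followed by GIST (60.2%), hepatocellular carcinoma (50%) and metastatic colorectal carcinoma (46.6" per cent. Section 2.3 then states: "There are no clinical or molecular risk factors that have been shown to predict those patients" who will develop HFSR.

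Section 3.1.1 admits solid tumours generally. Section 4.1 notes that "patients are referred from these outside disease centers (such as Sarcoma and GI"), and Section 5 lists the baseline data: "These will include age, gender, BMI, malignancy characteristics, smoking status" and others. Tumour type will therefore vary between patients and will be on file.

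**The concern.** When a baseline variable may be prognostic and is already collected, using it in the analysis normally buys some precision. It also protects the reading of the result if the arms happen to differ on that variable. The second benefit exists only if the adjustment is written down beforehand, because adjustment chosen after an imbalance is seen carries little weight.

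The trial is small: 35 per arm at most, with a futility look at 14 per arm. The two referral streams named in Section 4.1 plausibly fall on different sides of the Section 2.1 gradient: GIST and colorectal cancer differ by 60.2 − 46.6 = 13.6 points. Renal and colorectal differ by 71.4 − 46.6 = 24.8 points. The questions are how much the unadjusted test loses, and whether imbalance could mislead.

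**Working it through.** **1. The plan's own figures.** Inputs from Section 13.2: 35 per arm, 50% v 25%, one-sided 0.10.

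- Null SE = √(2 × 0.375 × 0.625 / 35) = 0.1157. Alternative SE = √((0.25 + 0.1875) / 35) = 0.1118.
- Power = Φ[(0.25 − 1.2816 × 0.1157) / 0.1118] = Φ(0.91) = 81.8%. Exact enumeration gives 80.9%; allowing for the futility look gives 78 to 79%. The stated 80% is reproduced.
- The null stopping probability at the look comes to 0.543, as stated.

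**2. How much of the outcome tumour type could explain.** The documents give neither the tumour mix nor grade 2+ rates by type. Assumption: the any-grade rates q are scaled proportionally so that the control mean m is 50% (or 40%, the lower end of the range in Section 13.2). With mix weights w:

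- Between-type variance Vb = Σw(q − m)²; share explained R² = Vb / [m(1 − m)].
- SD of the arm difference due to imbalance = √(2Vb / n).
- Colorectal/GIST 50:50, m = 0.5: rates 0.564 and 0.436, Vb = 0.0041, R² = 1.6%, SD at 35 per arm = 1.5 points.
- Renal/colorectal 50:50, m = 0.5: rates 0.605 and 0.395, Vb = 0.0110, R² = 4.4%, SD = 2.5 points.
- Over five assumed mixes, R² is about 1 to 4% and the SD 1.0 to 2.5 points. The unscaled renal/colorectal extreme gives 6.4% and 3.0 points.
- The total SE is √(0.5 / 35) = 12.0 points. In sample-size terms, 70 / (1 − R²) is worth about 1 to 5 patients.

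**3. Power by simulation** (no interim look, 50% v 25%, scaled rates, four assumed mixes: equal quarters; colorectal/GIST; colorectal-heavy; renal/colorectal):

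| Randomisation and test | Power |
|---|---|
| Simple, chi-squared | 80.8–81.0% |
| Simple, CMH by individual tumour type | 80.6–82.4% |
| Simple, CMH in two groups (colorectal + hepatocellular v GIST + renal) | 81.4–82.4% |
| Stratified by type, CMH by type | 81.6–82.3% |

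The gain is about 0.6 to 1.6 points for stratification plus CMH, and about 0.5 to 1.4 for the two-group CMH alone. CMH over all four types under simple randomisation can lose a fraction of a point when a type is sparse (80.9% to 80.6% in the colorectal-heavy mix), which is why two groups are preferable.

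Under the null, the chi-squared test rejects in about 9.4% of trials and CMH in about 10%. Part of the gain is therefore CMH using more of its nominal level.

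**4. A larger gap.** Assumptions: two groups in a 55:45 mix, the any-grade gap carried over whole, a constant 25-point effect, simple randomisation. Chi-squared v CMH power:

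- no gap: 81.0% v 81.2%
- 14-point gap: 80.9% v 82.0%
- 25-point gap: 80.9% v 83.8%

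**5. What imbalance can do at 35 per arm.**

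- Significance needs an observed difference of about 1.2816 × 0.1195 = 15.3 points. For a renal/colorectal imbalance alone to supply that, the shares would have to differ by 0.153 / 0.248 ≈ 60 points between arms.
- A 20-point difference in mix shifts the estimate by 0.20 × 14 ≈ 3 points or 0.20 × 25 = 5 points. Under the 55:45 assumption, 20 points or more occurs in 11.8% of trials, about 6% in each direction.
- Given such an imbalance favouring tazarotene and no true effect, the unadjusted false-positive rate is about 15% (14-point gap) or 20% (25-point gap); CMH stays near 10%.
- Given one against tazarotene and a true 25-point effect, unadjusted power falls to about 72% or 64%; CMH keeps about 80 to 83%.

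**6. At the futility look.** The boundary Z of 0.107 is an observed difference of 0.107 × √(0.5 / 14) = 2.0 points, against an SE of 18.9 points. Averaged over simple randomisation, the false-stop probability is 11.3%. With tumour mix perfectly balanced it is about 11% (14-point gap) or 10.5% (25-point gap). The average cost is under one point.

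**The case against.** The strongest reply is that randomisation already accounts for this. The unadjusted test is valid, its type I error is below nominal, and about one power point in a 70-patient signal-detection trial is not worth a change of primary test. That stands as to size: neither bias nor error inflation can be claimed.

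The evidence for the gradient is also thinner than it looks. The Section 2.1 rates are any-grade, while the primary endpoint is grade 2 or higher within 8 weeks. Nothing shows that the rates carry over to the dose-escalation schedule and urea background used here, and no rate is given for sarcoma other than GIST. It would be too strong to call tumour type a known predictor of the primary endpoint.

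Two stronger readings are tempting.

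- A reader might infer that chance imbalance could drive the result. It could not plausibly do so alone at 35 per arm: it adds 1 to 3 points of SD to an SE of 12.
- A reader might note that, at 14 per arm, the mix differs by 20 points or more (3 of 14) in 34% of trials, and link this to a false futility stop of 16% (14-point gap) or 20 to 21% (25-point gap). The figures describe different events. The 34% counts both directions; the higher stop rates need an adverse imbalance of 4 of 14. An adverse imbalance of 4 or more has probability 9.1%, and the mirror-image imbalance of 4 lowers the stop rate to about 7% or 4.5%.

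The reply does not remove the case for pre-specification. One randomisation will be observed, its tumour table will be visible, and only a rule fixed beforehand can answer questions about it. Adjustment costs essentially nothing if tumour type proves irrelevant (81.0% v 81.2%).

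**Conclusion.** The point holds as a low-cost improvement, not as a flaw that invalidates the design. The plan reports a tumour-type gradient and collects the variable, but uses it in neither allocation nor analysis. The average loss is about 0.6 to 1.6 power points under scaling to a 50% grade 2+ control rate, and about 3 under an assumed 25-point gap. The larger value lies in the roughly 12% of trials with a mix difference of 20 points or more, where the unadjusted test's conditional behaviour drifts and CMH's does not. All these sizes depend on an assumed tumour mix and on carrying any-grade differences over to grade 2+.

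Sections 2.1 and 2.3 also sit awkwardly together: one lists different rates by tumour type, the other says no clinical predictor has been shown.

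**What to change.** Before unblinding, by people who have not seen outcomes by arm:

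- In 13.1, make the final primary comparison a one-sided 0.10 CMH test stratified by two tumour groups, reported with the Mantel-Haenszel risk difference and its 90% interval. Keep the unadjusted chi-squared test and difference as sensitivity analysis.
- Define the two groups in advance. One option is colorectal, hepatocellular and other GI carcinoma v GIST, sarcoma, renal and other. Placing tumours for which the documents give no rate is a convention and should be labelled so.
- In 13.2 and 13.4, state that the interim futility rule stays on the chi-squared test as written. A futility-only look cannot raise the final type I error, so using a different test there does no harm to the 0.10 level.
- Show tumour type by arm in the baseline table.
- Reconcile 2.3 with 2.1, for example by saying that rates differ by tumour type but that this has not been established for grade 2+.

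Stratifying the remaining randomisation on the same two levels is optional: it adds little once the analysis is adjusted and means changing allocation during the trial.

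The cost is a few lines of SAP text, with no added patients, visits or procedures. The small downside is that a coarse two-level grouping must be fixed in advance.

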13.4 Interim Monitoring Plan

An interim look for futility will be performed, as above.

13.5 Analysis of Primary Endpoints

Please see 13.2 Analysis of Secondary Endpoints

Additional secondary endpoints include investigation of whether tazarotene plus BPS improves health-related quality of life associated with HFSR as assessed using Skindex-16 survey, dermatology quality life index (DLQI) and hand-foot syndrome 14-item scale (HFS-14) prior to initiating the TKI, then at 2-4 week intervals depending on the tool.

Secondary endpoints also include investigation of whether the intervention decreases global stress associated with HFSR as measured prior to initiating the TKI, then at 4 week intervals using the 10-item perceived stress scale (PSS), which has been validated in both healthy people and cancer patients.

The DLQI, Skindex-16 and HFSR are validated dermatologic tools that will be administered every 2 weeks and collect findings based on the past week. The PSS is based on the prior month and will be administered every 4 weeks. The PSS is a validated measure of global stress in cancer patients.

13.6 Reporting and Exclusions

13.6.1 Evaluation of Toxicity

All participants will be evaluable for toxicity from the time of their first treatment. The incidence of events that are new or worsening from the time of first dose of treatment will be summarized according to system organ class and/or preferred term, severity (based on CTCAE grade), type of adverse event, and relation to study treatment. Deaths reportable as SAEs and non-fatal serious adverse events will be listed by patient and tabulated by primary system organ class, and type of adverse event.

13.6.2 Evaluation of the Primary Efficacy Endpoint

Data will be analyzed based on intent-to-treat.

14. PUBLICATION PLAN

The results of this study will be made public within 24 months of reaching the end of the study follow up period, 24 weeks after the last patient initiates therapy.

15. APPENDIX A PERFORMANCE STATUS CRITERIA

ECOG Performance Status Scale		Karnofsky Performance Scale	
Grade	Descriptions	Percent	Description
0	Normal activity. Fully active, able to carry on all pre-disease performance without restriction.	100	Normal, no complaints, no evidence of disease.
		90	Able to carry on normal activity; minor signs or symptoms of disease.
1	Symptoms, but ambulatory. Restricted in physically strenuous activity, but ambulatory and able to carry out work of a light or sedentary nature (e.g., light housework, office work).	80	Normal activity with effort; some signs or symptoms of disease.
		70	Cares for self, unable to carry on normal activity or to do active work.
2	In bed <50% of the time. Ambulatory and capable of all self-care, but unable to carry out any work activities. Up and about more than 50% of waking hours.	60	Requires occasional assistance, but is able to care for most of his/her needs.
		50	Requires considerable assistance and frequent medical care.
3	In bed >50% of the time. Capable of only limited self-care, confined to bed or chair more than 50% of waking hours.	40	Disabled, requires special care and assistance.
		30	Severely disabled, hospitalization indicated. Death not imminent.
4	100% bedridden. Completely disabled. Cannot carry on any self-care. Totally confined to bed or chair.	20	Very sick, hospitalization indicated. Death not imminent.
		10	Moribund, fatal processes progressing rapidly.
5	Dead.	0	Dead.

16. APPENDIX B: TAZAROTENE OR PLACEBO DRUG DIARY

19-099

Drug Diary

Participant Study ID: _____
 Cycle: _____

Urea _____ % (if recommended by your oncologist)	Tazarotene or Placebo
Each morning, apply ½ fingertip to each palm & sole at 8:00 am (+/- 4 hours)	Each night, apply ½ fingertip unit (FTU) to each palm & sole at 8:00 pm (+/- 4 hours). If a dose is missed, it should be skipped entirely.

On the day that you start your Regorafenib dose and Tazarotene/placebo dose, please call the clinical research coordinator so that we can schedule your Day 15 appointment with us.

Clinical Research Coordinator
CRC phone: _____
CRC email: _____

Please indicate the date, time, amount taken and any comments in the dosing log below.

	Date	Urea	Tazarotene or Placebo	Comments about application
		Time of Daily Application	Time of daily Application	
Ex:	6/1/2009	8:00 am	8:00 pm	Itch on palm of left hand
Day 1				
Day 2				
Day 3				
Day 4				
Day 5				
Day 6				
Day 7				
Day 8				
Day 9				
Day 10				
Day 11				
Day 12				
Day 13				
Day 14				
Day 15				
Day 16				
Day 17				
Day 18				
Day 19				
Day 20				
Day 21				
Day 22				
Day 23				
Day 24				
Day 25				
Day 26				
Day 27				
Day 28				

17. APPENDIX C: EXAMPLES OF POTENT INHIBITORS OR INDUCERS OF CYTOCHROME P450 3A4

Examples of potent inhibitors or inducers of cytochrome P450 3A4		
	Potent inhibitors	Potent inducers
CYP3A	Boceprevir Cobicistat Conivaptan Danoprevir and ritonavir Elvitegravir and ritonavir Grapefruit juice Indinavir and ritonavir Itraconazole Ketoconazole Lopinavir and ritonavir Paritaprevir and ritonavir and (ombitasvir and/or dasabuvir) Posaconazole Ritonavir Saquinavir and ritonavir Telaprevir Tipranavir and ritonavir Troleandomycin Voriconazole Clarithromycin Diltiazem Idelalisib Nefazodon Nelfinavir	Carbamazepine Enzalutamide Mitotane Phenytoin Rifampin St. John's wort

Note: Strong inhibitors are drugs that increase the AUC of sensitive index substrates of a given metabolic pathway ≥ 5 -fold. Strong inducers are drugs that decrease the AUC of sensitive index substrates of a given metabolic pathway by $\geq 80\%$.

This table is prepared to provide examples of clinical inhibitors / inducers and is not intended to be an exhaustive list.

Table adapted from:

<https://www.fda.gov/drugs/developmentapprovalprocess/developmentresources/druginteractionslabeling/ucm093664.htm>

Drug-drug interactions data were collected based on a search of the University of Washington Metabolism and Transport Drug Interaction Database [Hachad et al. (2010), Hum Genomics, 5(1):61].

Participant Study ID: _____
Date Survey Completed: _____
Participant Signature: _____

NCI Protocol #: N/a
DF/HCC Protocol #: 19-099
Protocol Version Date: 22SEP2022

